7.1 Evaluation of efficacy

Objective tumor response and time to progression will be measured according to the RECIST criteria (version 1.1, Ref. 33).

Response criteria are essentially based on a set of measurable lesions identified at baseline as target lesions, and – together with other lesions that are denoted as non-target lesions – followed until disease progression.

Imaging datasets will be collected on an ongoing basis and reviewed retrospectively (details in section 15.4).

The following paragraphs are a quick reference to the RECIST criteria (version 1.1). The complete criteria are included in the published RECIST document [Ref. 33] also available at http://www.eortc.be/RECIST.

7.1.1 Measurability of tumor lesions at baseline

7.1.1.1 Definitions

- **Measurable disease** the presence of at least one measurable lesion. If the measurable disease is restricted to a solitary lesion, its neoplastic nature should be confirmed by cytology/histology.
- Measurable lesions tumor lesions that can be accurately measured in at least one dimension (longest diameter to be recorded) as ≥ 20 mm with chest x-ray, and as ≥ 10 mm with CT scan or clinical examination [using calipers]. Bone lesions are considered measurable only if assessed by CT scan and have an identifiable soft tissue component that meets these requirements (soft tissue component > 10 mm by CT scan). Malignant lymph nodes must be ≥ 15 mm in the short axis to be considered measurable; only the short axis will be measured and followed. All tumor measurements must be recorded in millimeters (or decimal fractions of centimeters) by use of a ruler or calipers. Tumor lesions situated in a previously irradiated area, or in an area subjected to other loco-regional therapy, are usually not considered measurable unless there has been demonstrated progression in the lesion.
- Non-measurable lesions All other lesions (or sites of disease), including small lesions are considered
 non-measurable disease. Bone lesions without a measurable soft tissue component, leptomeningeal
 disease, ascites, pleural/pericardial effusions, lymphangitis cutis/pulmonis, inflammatory breast
 disease, lymphangitic involvement of lung or skin and abdominal masses followed by clinical
 examination are all non-measurable. Nodes that have a short axis <10 mm at baseline are considered
 non-pathological and should not be recorded or followed.
- Target Lesions. When more than one measurable tumor lesion or malignant lymph node is present at baseline all lesions up to a maximum of 3 lesions total (and a maximum of 2 lesions per organ) representative of all involved organs should be identified as target lesions and will be recorded and measured at baseline. Target lesions should be selected on the basis of their size (lesions with the longest diameter), be representative of all involved organs, but in addition should be those that lend themselves to reproducible repeated measurements. Note that pathological nodes must meet the criterion of a short axis of ≥ 15 mm by CT scan and only the short axis of these nodes will contribute to the baseline sum. At baseline, the sum of the target lesions (longest diameter of tumor lesions plus short axis of lymph nodes: overall maximum of 3) is to be calculated and recorded.
- Non-target Lesions. All non-measurable lesions (or sites of disease) including pathological nodes (those with short axis ≥ 10 mm but < 15 mm), plus any measurable lesions over and above those

listed as target lesions are considered *non-target lesions*. Measurements are not required but these lesions should be noted at baseline and should be followed as "present" or "absent".

All baseline evaluations should be performed as closely as possible to the beginning of treatment and never more than 4 weeks before the beginning of the treatment.

7.1.1.2 Methods of measurements

The same method of assessment and the same technique should be used to characterize each identified and reported lesion at baseline and during follow-up. Assessments should be identified on a calendar schedule and should not be affected by delays in therapy, which may be treatment arm dependent. While on study, all target lesions recorded at baseline should have their actual measurements recorded on the CRF at each subsequent evaluation, even when very small (e.g. 2 mm). If it is the opinion of the radiologist that the lesion has likely disappeared, the measurement should be recorded as 0 mm. If the lesion is believed to be present and is faintly seen but too small to measure, a default value of 5 mm should be assigned. For lesions which fragment/split add together the longest diameters of the fragmented portions; for lesions which coalesce, measure the maximal longest diameter for the "merged lesion".

- Clinical Lesions. Clinical lesions will only be considered measurable when they are superficial and ≥ 10 mm as assessed using calipers (e.g. skin nodules). For the case of skin lesions, documentation by color photography including a ruler to estimate the size of the lesion is recommended. If feasible, imaging is preferred.
- Chest X-ray. Chest CT is preferred over chest X-ray, particularly when progression is an important endpoint, since CT is more sensitive than X-ray, particularly in identifying new lesions. However, lesions > 20 mm on chest X-ray may be considered measurable if they are clearly defined and surrounded by aerated lung.
- CT, MRI. CT is the best currently available and reproducible method to measure lesions selected for response assessment. This guideline has defined measurability of lesions on CT scan based on the assumption that CT slice thickness is 5 mm or less. When CT scans have slice thickness greater than 5 mm, the minimum size for a measurable lesion should be twice the slice thickness. MRI is also acceptable in certain situations (e.g. for bone scans). While PET scans are not considered adequate to measure lesions, PET-CT scans may be used providing that the measures are obtained from the CT scan and the CT scan is of identical diagnostic quality to a diagnostic CT (with IV and oral contrast).
- Cytology, Histology. These techniques can be used to differentiate between PR and CR in rare cases if
 required by protocol (for example, residual lesions in tumor types such as germ cell tumors, where
 known residual benign tumors can remain). When effusions are known to be a potential adverse
 effect of treatment (e.g. with certain taxane compounds or angiogenesis inhibitors), the cytological
 confirmation of the neoplastic origin of any effusion that appears or worsens during treatment when
 the measurable tumor has met criteria for response or stable disease is advised to differentiate
 between response or stable disease and progressive disease.

7.1.2 Tumor response evaluation

All patients will have their BEST RESPONSE from the start of study treatment until the end of treatment classified as outlined below:

Complete Response (CR): disappearance of all *target* and *non-target* lesions and normalization of tumor markers. Pathological lymph nodes must have short axis measures < 10mm (Note: continue to record the measurement even if < 10 mm and considered CR). Tumor markers must have normalized. Residual lesions (other than nodes < 10 mm) thought to be non-malignant should be further investigated (by cytology or PET scans) before CR can be accepted.

Partial Response (PR): at least a 30% decrease in the sum of measures (longest diameter for tumor lesions and short axis measure for nodes) of target lesions, taking as reference the baseline sum of diameters. Non target lesions must be non-PD.

Stable Disease (SD): Neither sufficient shrinkage to qualify for PR nor sufficient increase to qualify for PD taking as reference the smallest sum of diameters on study.

Progressive Disease (PD): at least a 20% increase in the sum of diameters of measured lesions taking as references the smallest sum of diameters recorded on study (including baseline) AND an absolute increase of ≥ 5 mm. Appearance of new lesions will also constitute PD (including lesions in previously unassessed areas). In exceptional circumstances, unequivocal progression of non-target disease may be accepted as evidence of disease progression, where the overall tumor burden has increased sufficiently to merit discontinuation of treatment, for example where the tumor burden appears to have increased by at least 73% in volume (which is the increase in volume when all dimensions of a single lesion increase by 20%). Modest increases in the size of one or more non-target lesions are NOT considered unequivocal progression. If the evidence of PD is equivocal (target or non-target), treatment may continue until the next assessment, but on further documentation, the earlier date must be used.

Table 1: Integration of Target, non-Target and New lesions into response assessment

Target Lesions	Non-Target Lesions	New Lesions	Overall Response	Best Response for this category also requires						
Patients with Target	Patients with Target lesions ± non target lesions									
CR	CR	No	CR	Normalization of tumor markers, tumor nodes < 10 mm						
CR	Non-CR/Non-PD	No	PR							
CR	Not all evaluated	No	PR							
PR	Non-PD/ not all evaluated	No	PR							
SD	Non-PD/ not all evaluated	No	SD	documented at least once ≥ 8 wks. from baseline						
Not all evaluated	Non-PD	No	NE							
PD	Any	Any	PD							
Any	PD	Any	PD							
Any	Any	Yes	PD							

Note: Patients with a global deterioration of health status requiring discontinuation of treatment without objective evidence of disease progression [or evidence of unequivocal disease progression] at that time should be reported as "symptomatic deterioration". This is a reason for stopping therapy, but is NOT objective PD. Every effort should be made to document the objective progression even after discontinuation of treatment.

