4.1 Treatment beyond progression

The local investigator may choose to continue treatment with osimertinib beyond RECIST 1.1 PD, if, in their opinion, the patient continues to receive clinical benefit. However, this should be discussed with the EORTC HQ. Information on post-PD treatment needs to be provided to EORTC HQ and follow-up must follow chapter 6 according to the treatment arm.

In case of oligo-progressive disease (please refer to chapter 0) in a known metastatic lesion local therapy (radiotherapy / surgery / cryotherapy) will be allowed after mandatory discussion with EORTC headquarters. This procedure will be reported in the CRF. Information on post-PD treatment needs to be provided to EORTC HQ and follow-up must follow chapter 6 according to the treatment arm.

5 Therapeutic regimens, expected toxicity, dose modifications

Osimertinib (AZD9291) and gefitinib are considered as Investigational Medicinal Products.

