5.5 Withdrawal criteria

Whatever the disease status, the treatment will always be discontinued in case of

- AE or intercurrent illness that, in the opinion of the investigator, warrants the patient's withdrawal from study treatment;
- Patient refusal or lost to follow-up;
- Excessive toxicity precluding further therapy, according to the responsible physician;
- Any adverse events specified as a reason for permanent discontinuation as defined in the guidelines for dose modification due to AE in section 5.6 and subsections

- Significant non-compliance/non-adherence with the protocol schedule in the opinion of the investigator or the sponsor;
- PD according to RECIST 1.1 to osimertinib; continuation of osimertinib post-PD is allowed on individual basis provided that in the opinion of treating physician, patient may benefit from this therapy;
- Pregnancy;
- Start of a new anticancer treatment.

Patients discontinuing therapy not according to the protocol should not receive any other cancer treatment before their disease progresses, unless this is clearly not in the interest of the patient according to the local investigator.

After progression to osimertinib, the treatment will be left to the discretion of the treating physician. Any anti-cancer therapy other than the study drug given as single agent will not be considered as part of the protocol treatment.

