6.1.3 At the end of treatment

Treatment is continued until objective PD to osimertinib according to RECIST 1.1, or other discontinuation criteria are met (such as toxicity, patient refusal, etc) please refer to sections 5.4 and 5.5.

When the treatment is decided to be permanently stopped, an end of treatment visit needs to be performed at 30 days after last protocol treatment (+/- 7 days) and the following assessments are required:

- Adverse event collection;
- Performance Status and clinical examination including vital signs, height, weight and blood pressure;
- Collection of concomitant medication;
- In case objective progression as per RECIST 1.1 and an optional tissue biopsy can be performed, results will be collected in the study.

A 28-day follow-up LVEF assessment by MUGA or ECHO will be required if an on-treatment assessment was abnormal at the time of discontinuation of study treatment, to confirm reversibility of the abnormality.

Patients who discontinue study drug for reasons other than objective disease progression will additionally continue assessments for objective PD; please refer to section 6.1.2.4.

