7.2.6 Overall Response Rate (ORR) to osimertinib

Overall Response Rate (ORR) to osimertinib is an overall rate including patients with documented complete response (CR) or partial response (PR) while patients are receiving osimertinib, where CR and PR are defined according to the principles mentioned in section 7.1.2. Patients not receiving osimertinib will not be included in the ORR to osimertinib analysis.

The nature of this endpoint is different in Arm A (first line ORR) from Arm B and C (second line ORR).

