7.2.7 Treatment duration

Treatment duration will be measured from the time of randomization until the protocol treatment stops. In Arms B and C, if patients receive osimertinib, the duration is calculated till osimertinib stops.

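### Secondary ORR only: the best-response window has no stop at first RECIST progression on osimertinib, so a later scan could be scored as a response

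*Combined protocol and SAP*

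**What the plan says.** **Response window.** Section 7.1.2: "All patients will have their BEST RESPONSE from the start of study treatment until the end of treatment classified as outlined below". Section 7.2.6 defines ORR to osimertinib through "documented complete response (CR) or partial response (PR) while patients are receiving osimertinib" and leaves out patients who never receive the drug.

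**When treatment ends.** The default is in section 6.1.3, repeated in 6.2.4 and 6.3.4: "Treatment is continued until objective PD to osimertinib according to RECIST 1.1, or other discontinuation criteria are met". Section 5.5 adds an exception: "continuation of osimertinib post-PD is allowed on individual basis provided that in the opinion of treating physician, patient may benefit from this therapy". Sections 4.1, 5.3 and 5.4 say the same in substance. On treatment after progression, section 5.5 states: "Any anti-cancer therapy other than the study drug given as single agent will not be considered as part of the protocol treatment". For the separate endpoint of treatment duration, section 7.2.7 states: "In Arms B and C, if patients receive osimertinib, the duration is calculated till osimertinib stops".

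**Scans after progression.** For patients treated beyond progression, section 4.1 requires that "follow-up must follow chapter 6 according to the treatment arm". Chapter 6 schedules CT every 8 weeks on osimertinib. In arm A (6.1.2.4) it runs until osimertinib has ended and a second progression is documented. Section 7.1.1.2 has target lesions measured at every later evaluation on study.

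**Local therapy.** For oligoprogression, section 4.1 says that "in a known metastatic lesion local therapy (radiotherapy / surgery / cryotherapy) will be allowed after mandatory discussion with EORTC headquarters". Section 5.7.4 also permits it when a known lesion progresses on osimertinib.

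**Analysis.** Under Response Rate, section 8.2.2 treats the categories progression, early death and unknown as non-response, and plans a two-sample test of response rates at the 5% two-sided level between two arms that it does not name. The opening of section 8.2 reserves between-arm comparisons for BPFS.

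**The concern.** A response rate to a drug is normally read as the share of patients whose tumour shrank before the drug failed. Here the window is tied to stopping treatment, and the protocol lets some patients continue after failure and keeps measuring them. For those patients alone, the written rule lets a scan after progression supply the best response. The shrinkage could come from a late effect of osimertinib or from local treatment of the lesion that grew.

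The error can go in one direction only. A patient who responded before progression is already a responder, so later scans can only turn non-responders into responders. At stake are the secondary ORR estimate in each arm and the response-rate test in section 8.2.2.

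**Working it through.** **1. Plan figures.** The plan states no ORR assumption, sample size or power, so there is no figure to reproduce for this point. As a side check, the 25-of-49 rule has exact binomial alpha 0.0776 at a true rate of 40% and power 0.9224 at 60%, against the stated 0.08 and 92%. Nothing in that calculation uses ORR.

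**2. When the window closes.**
- Patient stopped at progression on osimertinib (the default): treatment ends there, so sections 7.1.2 and 7.2.6 close the window at about the right place.
- Patient continued under section 4.1 or 5.5: treatment ends later and the patient is still receiving osimertinib, so both sections keep the window open. Section 5.5 puts outside protocol treatment only therapy other than single-agent study drug.

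**3. Whether a scan after progression can meet the PR rule.** Assumed example in arm A: two target lesions, no new lesion, non-target disease not progressing. The rules come from section 7.1.2: PR is a fall of 30% or more from the baseline sum; PD is a rise of 20% or more from the smallest sum and of 5 mm or more.

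| Scan | Lesions (mm) | Sum (mm) | Change | Category |
|---|---|---|---|---|
| Baseline | 40 + 20 | 60 | – | – |
| Best before PD | 34 + 16 | 50 | (50 − 60)/60 = −16.7% | SD |
| Progression | 34 + 30 | 64 | (64 − 50)/50 = +28%, +14 mm | PD |

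The PR limit is 0.70 × 60 = 42 mm.
- *No local therapy:* the sum must fall from 64 to 42 mm, which is 22/64 = 34% of its value at progression.
- *Local therapy to the 30 mm lesion, the other unchanged:* the treated lesion must measure 42 − 34 = 8 mm or less, a reduction of (30 − 8)/30 = 73%. Section 7.1.1.2 records a vanished lesion as 0 mm, giving (34 − 60)/60 = −43.3%. A lesion too small to measure is recorded as 5 mm, giving (39 − 60)/60 = −35.0%. Both are PR.

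**4. Where the route is closed.**
- A new lesion gives PD in Table 1 whatever the targets do. Section 7.1.3 defines oligoprogression by up to three new lesions, so those patients stay at PD.
- Section 7.1.1.1 usually treats a lesion in a locally treated area as non-measurable, with an exception for demonstrated progression, and it sits under a baseline heading. If the treated target is not evaluated and there is no PD elsewhere, Table 1 gives NE, not PR. The local-therapy route therefore needs a known target that is still scored as measurable.
- Patients with CR or PR before progression are unaffected.

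**5. Size.** Each patient scored this way adds 1/n to an arm's ORR.
- Arm A at the planned n = 49: 1/49 = 2.0 points.
- Arms B and C count only patients who received osimertinib, a number not given. Assuming 70–90% of 49, n is 34 to 44, and each patient adds 1/44 = 2.3 to 1/34 = 2.9 points.
- For scale, with an assumed 34 responders of 49, ORR is 69.4% (exact 95% CI 54.6 to 81.7). One extra responder makes it 71.4% (56.7 to 83.4); three make it 75.5% (61.1 to 86.7).

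**The case against.** The best counter-argument is that the protocol, read as a whole, already implies a stop. The introduction to section 7.1 describes lesions as followed up to progression. The end-of-treatment sections and section 5.5 make progression on osimertinib the default end. Section 4.1 labels what follows as post-progression treatment. Section 8.2.2 counts the progression category as non-response. Section 7.1 also calls its text a quick reference to the published RECIST document, and section 15.4.4 points to a central review charter. I had neither document, and either may set a stop.

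Part of this stands. The default does close the window for patients who stop at progression, and section 7.2.7 is weak support because it defines a different endpoint. The rest does not close the window for patients who continue. The sentence in 7.1 is a general introduction. It conflicts with the scans that 4.1 and 6.1.2.4 require after progression, and it cannot be literal in arms B and C for patients switched at RECIST progression on gefitinib. The non-response rule in 8.2.2 acts on the category assigned and does not say that progression overrides a later PR. If RECIST or the charter does supply a stop, the protocol's stated window still says otherwise and should be brought into line.

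The objection that the route is narrow also stands: without local therapy it needs a substantial late fall on the same drug, and with local therapy it needs one particular scoring choice.

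**Conclusion.** The point holds as a minor defect in a secondary endpoint. Followed as written, sections 7.1.2 and 7.2.6 allow a patient kept on osimertinib after RECIST progression, with no earlier response and no new lesion, to be scored CR or PR on a later scan. The effect is upward only, 2.0 points per patient at n = 49. This is a per-patient effect, not an estimate of bias.

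Three stronger readings are tempting, and the documents do not support them.
- *That ORR in this trial will be inflated, or that one arm will be favoured.* No rate of treatment beyond progression or of local therapy is given for any arm. The number affected may be zero.
- *That local therapy will readily produce responses.* New-lesion oligoprogression stays PD, and a treated target may be NE.
- *That the primary result is at risk.* Section 7.1.2.2 dates progression at the first day the criteria are met, and after a switch PFS-OSI uses progression on osimertinib. Later scans therefore leave PFSR-OSI-18, PFS-OSI and the 25-of-49 rule unchanged.

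A reader might also infer the opposite: that the effect stops at each arm's own estimate because only BPFS is compared. Section 8.2 says so, but the Response Rate paragraph of 8.2.2 plans a two-sample test, which would inherit any shift. The plan is inconsistent on this.

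**What to change.** In section 7.2.6, with a cross-reference from 7.1.2, state that best response to osimertinib uses assessments from the first osimertinib dose up to and including the first RECIST 1.1 progression on osimertinib, or up to the start of other anticancer therapy if that is earlier, and that later assessments do not count toward ORR.

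The stop should be tied to progression on osimertinib. A stop at the first progression after randomization would remove the second-line response rate in arms B and C for patients switched at RECIST progression. A separate rule for local therapy is not needed, because sections 4.1 and 5.7.4 allow it only once progression has occurred.

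The cost is one sentence, one cross-reference and a matching change to the response derivation. No new data are needed and no design figure changes. The downside is that a rare true late shrinkage on osimertinib after progression would no longer count as a response.
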